5.3 Progression criteria

The primary outcome of the pilot cRCT will be whether progression to a Phase III RCT is justified in terms of pre-specified progression criteria:

- 1 The intervention is implemented with fidelity in at least 3 of 4 intervention settings
- 2 The process evaluation indicates the intervention is acceptable to students, FE staff and public health commissioners (measured by qualitative interview, routine monitoring data on attendance and survey data).
- 3 At least 5 of the 6 FE settings are retained throughout the study
- 4 Using a traffic light system; at least 60% of students approached complete the student questionnaire at baseline and follow-up to progress (green); Amber indicates a response rates of between 50-60% = progress amending the data collection protocols; Red indicates a response rates of less than 50% = do not progress.

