7.2 Randomisation

No randomisation will occur during Phase 1 or 2. In the pilot trial, randomisation will occur after all settings have completed baseline data collection. Clusters (settings) will be randomised to receive either the SaFE intervention or usual practice. Following baseline surveys (Sep/Oct 2020), the trial statistician will randomly allocate settings into 2 arms using a 2:1 ratio: SaFE delivered in 4 settings, and usual practice in 2. The allocation will be stratified by country and type of setting. Recruitment will take place between January and July 2020.

Development and Evaluation of Complex Interventions for Public Health Improvement A UKCRC Public Health Research Centre of Excellence

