7.3 Student recruitment rates

All students aged 16 or over at participating sites will be eligible to take part. We will use a repeated cross-sectional design in the pilot cRCT for three reasons: 1) the intervention aims to operate at the FE level and is expected to impact on all students, not just on those who were present at baseline; 2) the NIHR PHR funded Filter study found that, in FE settings, high turnover of students, irregular days of student attendance and lack of accurate student enrolment data, prevent the creation of an accurate sampling frame; [58] 3) in cRCTs, when migration into or out of the clusters is high over time, the baseline cohort may not remain representative of the cluster and therefore repeated cross-sectional analysis is preferred to minimise bias. This approach has been used in previous school based cRCTs. [59] The sampling frame will be defined as the number of students approached during data collection time periods. Response rates will be calculated as number of completed questionnaires.

8 Consent and retention

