13.2 Blinding

In the pilot cRCT all parties will be blind to allocation during the baseline data collection. It is not possible for study participants (students), teachers, trial managers, the intervention delivery team or researchers involved in the process evaluation to be blind to intervention status. However, fieldworkers at outcome data collections will remain blind to intervention status as will the statistician analysing the primary and secondary outcome data and the health economists undertaking the economic analysis. If school/college allocation becomes apparent during interactions with schools we will record this.

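### Progression criterion 4 sets one response rate that names no arm, so with 4 SaFE and 2 control settings it can be green while the control arm is in the red band at follow-up

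*Protocol*

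**What the plan says.** Protocol section 5.3 makes the pilot's primary outcome a decision on progression against four criteria. Criterion 4 is the only one on student response. Green is "at least 60% of students approached complete the student questionnaire at baseline and follow-up to progress (green". The other bands are "Amber indicates a response rates of between 50-60% = progress amending the data collection protocols" and "Red indicates a response rates of less than 50% = do not progress". Criteria 1 and 3 count settings (3 of 4 delivered with fidelity, 5 of 6 retained), and criterion 2 concerns acceptability. None refers to response by arm.

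Section 7.3 supplies the rate: "The sampling frame will be defined as the number of students approached during data collection time periods" and "Response rates will be calculated as number of completed questionnaires". Again no arm or setting is named. The same section fixes a repeated cross-sectional design.

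Section 7.2 gives the allocation, "SaFE delivered in 4 settings, and usual practice in 2", and the timing, "randomisation will occur after all settings have completed baseline data collection". Section 13.2 says of blinding: "It is not possible for study participants (students), teachers, trial managers" and others to be blind to intervention status, but it keeps fieldworkers at outcome data collection blind.

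Section 14.1 places student response and follow-up in a CONSORT flow diagram, tabulates them by socioeconomic disadvantage, and gives feasibility outcomes with 95% confidence intervals. It attaches no progression rule to a between-arm comparison of response.

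**The concern.** Because randomisation follows the baseline survey, allocation can affect response only at follow-up. Those respondents are a fresh cross-section, invited after allocation in settings where students and teachers know whether SaFE is running. SaFE settings also have a champion, publicity and staff training (sections 10.1 and its delivery text), any of which might change willingness to fill in a questionnaire on sex and relationship violence.

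A single rate over all students approached gives the SaFE settings most of the weight. Good response there can hide poor response in the control settings. If that happened, the pre-specified rule would report that data collection works, although one arm had fallen below the level at which the protocol itself says not to progress. The indicative Phase III primary outcomes are self-reported (section 5.4), so the Phase III team would want to know this before keeping the data collection methods unchanged.

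**Working it through.** **Inputs.** Bands of 60% and 50% (section 5.3); 4 SaFE and 2 control settings (section 7.2). The protocol gives no expected response rate or number approached, and section 13.3 has no power calculation, so there is no stated figure to reproduce. Assumption: equal numbers approached per setting, so the control share of students approached is w = 2/6 = 1/3. Section 4 says sites vary considerably in size, so w from 20% to 50% is shown as well.

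**Pooled rate.** Pooled = (1 − w)·S + w·C, where S and C are the SaFE and control response rates. At w = 1/3 this is (4S + 2C)/6.
- S = 70%, C = 40%: (280 + 80)/6 = 60.0%. Green, control red.
- S = 66%, C = 49%: (264 + 98)/6 = 60.3%. Green, control red.

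**SaFE rate needed for a pooled 60%.** S = (0.60 − w·C)/(1 − w).

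| Control rate | w = 20% | w = 1/3 | w = 50% |
|---|---|---|---|
| 49% | 62.8% | 65.5% | 71% |
| 45% | 63.8% | 67.5% | 75% |
| 40% | 65% | 70% | 80% |

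At the boundary C = 50%, S must be 62.5%, 65% and 70%. The gap beyond which green and a red control arm can coexist is therefore about 12.5, 15 and 20 points.

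**A second reading of criterion 4.** The above treats follow-up as having its own rate. If baseline and follow-up were combined into one rate with equal numbers, a 65% baseline would need only 2 × 60 − 65 = 55% at follow-up. SaFE 58% and control 49% give (232 + 98)/6 = 55%, so a gap of 9 points would suffice.

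**Does the gap itself produce bias?** Take true relationship violence of 50% in both arms (the section 4 background figure). The response rates below are assumed.
- SaFE 70% and control 40%, each unrelated to outcome: measured 50% v 50%, no bias.
- SaFE 70% regardless of outcome; control 34% in cases and 46% in non-cases (40% overall): control measures 0.34/(0.34 + 0.46) = 42.5%, a false 7.5 points.
- SaFE 60% regardless of outcome; control 51% in cases and 69% in non-cases (60% overall): control measures 0.51/(0.51 + 0.69) = 42.5%, the same 7.5 points with equal response.

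The bias comes from response depending on outcome in one arm and not in the other, not from the size of the gap.

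**Cost of a 50% floor in each arm.** Normal approximation by simulation, true response 65% in every setting, SaFE mean over 4 settings, control mean over 2, equal numbers approached. The between-setting SD is an assumption.

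| SD | Either arm <50% | Pooled ≥60% and either arm <50% |
|---|---|---|
| 8 points | 0.4% | 0.2% |
| 10 points | 1.8% | 0.7% |
| 15 points | 10.0% | 3.1% |

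The last column is the chance of a needless downgrade. The middle column also counts runs that were not green anyway.

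**What the floor misses.** S = 80%, C = 51% is a gap of 29 points, pooled (320 + 102)/6 = 70.3%, and stays green. With true rates of 70% and 55% and SD 10, the mean of two control settings falls below 50% with probability Φ((50 − 55)/(10/√2)) = 24%.

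**The case against.** The strongest reply is that criterion 4 is a feasibility threshold for data collection, for which an overall rate is a reasonable choice. None of the section 5.2 objectives compares response between arms, section 12.3 says the pilot is not powered for intervention effects, and two control settings cannot establish that differential response is absent. Blinded fieldworkers invite the students (sections 13.2 and 15.1), and the prize draw and the £500 setting payment are not tied to arm. The CONSORT diagram would normally split response by arm, so a gap would probably be seen, and the SAP may say more.

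Much of this stands. The protocol contradicts nothing here, and pooling is the plain reading of a rule that names no arm, not the protocol's own word. Two control settings cannot separate an allocation effect from one poorly responding setting. Blinded fieldworkers reduce the risk, although they do not make students or teachers blind.

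It does not remove the point. The bands are fixed in section 5.3 as the pilot's primary outcome, so they are not detail left to the SAP. A gap visible in a diagram triggers nothing, and the rule would still return green.

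A reader might go further and infer that a red control arm would itself bias a Phase III comparison. The documents do not support that: as the working shows, a 30-point gap can give no bias and equal response can give 7.5 points. Nor does the protocol say that demonstrating equal response is a purpose of the pilot.

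**Conclusion.** The point holds as a gap in the decision rule. Criterion 4 can be green with the control arm in the red band at follow-up once the arms differ by about 15 points, assuming equal numbers approached per setting (about 12.5 to 20 points for control shares of 20% to 50%). Unequal response could bias a later comparison of self-reported outcomes, but only if responding relates to outcome differently by arm, which the gap alone cannot show. The protocol gives no reason to expect such a gap; the finding is that the rule would not act on one. This is an inexpensive improvement to the progression rule, not an error that invalidates the pilot.

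**What to change.** Add to criterion 4 in section 5.3: *Green also requires a follow-up response rate of at least 50% in the SaFE arm and in the control arm; if either is lower, the result is amber at best.*

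Add to section 14.1: *Follow-up response will be reported by arm and by setting, with the between-arm difference and a 95% confidence interval that allows for clustering, and will be considered in the progression decision.* This second sentence is needed because the floor does not detect a large gap above 50%. The interval will be wide. With an assumed setting SD of 10 points, the standard error is 10 × √(1/4 + 1/2) = 8.7 points, and with 6 − 2 = 4 degrees of freedom the half-width is 2.776 × 8.66 = 24 points. It can inform judgement but cannot show that a difference is absent.

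The cost is two sentences and no new data, provided numbers approached are logged by setting. The chance of a needless downgrade is about 0.2% to 0.7% at SD 8 to 10 points and about 3% at SD 15, if true response is 65% everywhere. Capping at amber, and not stopping, is deliberate: a low control rate may reflect one of only two settings, and amber leads to amended data collection, not to a halt.

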5.4 Pilot primary outcomes measures

In the pilot cRCT, we will examine the indicative proposed primary outcomes of a future Phase III trial:

- Unprotected intercourse at last intercourse measured using validated questions from the SHARE questionnaires.[64] Unprotected intercourse will be defined as vaginal or anal (not oral) intercourse that involves no reliable method of STI and/or pregnancy prevention (i.e., reliable meaning STI prevention (e.g. condoms) and pregnancy prevention (e.g. condoms or other contraceptives if involving a woman)).
- Self-report experience of DRV victimisation in the last 12 months (measured at baseline and 12month follow up) using sCADRI.[65] Self-report has been used because most episodes of DRV will not result in notification to the school, police or NHS,[66] and our intervention is likely to increase rates of such notifications with the risk of ascertainment bias. While the intervention may result in increased self-report, measurement error will be minimised by using validated and reliable measures, comprising items focussed on specific behaviours. The 'CADRI' comprises 92 items assessing DRV victimisation (and perpetration) over the past two months.[67] Subscales cover emotional abuse, relational abuse, controlling behaviours, physical violence, and nonconsensual sexual activities. Research has found that DRV measured using 'CADRI' is correlated during adolescence with early sexual debut, unsafe sex, violence and suicidal ideation.[68] The 'CADRI' has been used in research with young people in US and Canadian studies.[69,70] However, due to problems with its use in trials due to its length, a 10-item version of 'CADRI' (sCADRI) has been developed and piloted among school-based samples of 9-12th graders and atrisk samples in Canada.[65] It is also being piloted for use in UK samples of young people aged up to 16 in our NIHR PHR funded pilot trial of Project Respect. [71] This new measure was found to be slightly less sensitive than the full questionnaire but to have good reliability, fit and convergent validity with the full measure.[65] We plan to use this short version, adapting it for measurement of DRV in the last 12 months and adding items from the original 'CADRI' to assess experience of controlling behaviours.

5.5 Pilot secondary outcomes measures

Informed by our logic model, the indicative secondary outcomes in a Phase III RCT will be;

- STI and pregnancy prevention methods used at last intercourse (measuring use of condoms or hormonal contraceptives at first sexual intercourse is not appropriate given higher rates of sexual debut in FE than school based samples);[64,72]
- Use of emergency contraception at last intercourse;[64,72]
- STI testing and diagnosis in the last 12 months;[64,72]
- Self-reported pregnancy and unintended pregnancy (initiation of pregnancy for men) in the last 12 months;[64,72]

Centre for **Trials Research** Canolfan

- Sexual regret at last intercourse using measures from the Avon Longitudinal Study of Parents and Children (ALSPAC);[73]
- Sexual harassment taking place at FE settings in the last 12 months using measures taken from the School Health Research Network survey [74] and Hostile Hallways survey;[75]
- Non-volitional sex in the last 12 months using measures from the National Survey of Sexual Attitudes and Lifestyles (NATSAL);[76]
- DRV perpetration in the last 12 months using the sCADRI [65] as described above; ٠
- EQ-5D-5L to measure health-related quality of life and;
- Self-reported awareness of services, and help seeking for victims and perpetrators will be • assessed by existing measures.[77]

We will assess the feasibility of data linkage comprising of three parts; 1) We will consult with data providers to understand their requirements for data linkage, associated costs, data transfer/storage requirements, fair processing (including participant facing materials; consent material, information sheet), timescales for data release and available data. Sexual Health Clinic, GP and Department of Health data relating to identification and treatment of STIs, pregnancy, abortion and emergency contraception prescriptions will be considered. Sensitive sexual health information has previously been successfully linked (e.g. data on abortions).[78] The logistics of linking, transferring and data storage will also form this feasibility assessment, including governance requirements of multiple data providers. This will identify the practical and associated costs for future data linkage in a phase III trial. 2) We will ask participants to provide their identifiers (name, DOB, postcode) and explore consent rates to data linkage to routinely collected sexual health data, as well as exploring consent rates by age, sex and socioeconomic status (SES) and outcomes to quantify any selection bias. To calculate SES we will request student postcodes to derive an area-level measure of deprivation, household status and employment status (where relevant). Separate information and consent materials will be developed in line with data provider requirements and participants will be able to decline data linkage whilst continuing with the study. Data will not be accessed in the pilot cRCT as there would be too few outcomes (e.g. abortions) with the expected sample size. However, understanding the acceptability of linking to routine data will inform the requirements for any future trial. 3) We also propose to ask participants to provide their identifiers and consent to enable their data to be linked at the two time points. Participants will be asked to opt-into the longitudinal sample and provide identifiers and consent at the end of the questionnaire. The rates of consent and the proportion of students retained from baseline to follow-up will inform whether we would conduct an exploratory longitudinal analysis in a phase III trial.

6. Study design

6.1 Design

Intervention optimisation, feasibility testing and a pilot cRCT with integrated process and economic evaluations (MRC complex intervention phase II study).

Stage 1: Optimisation of training and publicity materials and an intervention manual for the SaFE intervention;

Stage 2: Feasibility testing in two FE settings followed by a period of refinement of the interventions; Stage 3: 2-arm pilot trial with cluster randomisation (at the level of FE setting) in 6 FE settings in England and Wales with an embedded process evaluation.

6.2 Risk assessment

A Trial Risk Assessment has been completed by the SaFE Study Manager to identify the potential hazards associated with the trial and to assess the likelihood of those hazards occurring and resulting in harm. A copy of the trial risk assessment may be requested from the SaFE Study Manager.

Risks: Some individuals might find aspects of intervention content or research upsetting if they, or a significant other, have experienced a problem relating to DRV, a pregnancy, or their sexual health. The trial manager will work with FE settings to ensure a system is in place to provide appropriate support in such circumstances. Research participants will be informed that participation is voluntary and that they may withdraw at any point. All students will be signposted to support services, including college safeguarding leads. We will minimise disruption for staff and ensure student privacy and confidentiality by employing previously successful strategies used in the SaFE intervention development study.[48] As with any health intervention, there is a risk of widening health inequalities if the students that are exposed to the intervention are at a lower risk of DRV or poor sexual health. In the pilot cRCT, we will be underpowered to test for differences in the effectiveness of SaFE by socioeconomic inequalities. Any potential for unintended harmful or iatrogenic effects due to the intervention itself will also be explored via the collection and analysis of qualitative data.

7. FE setting and participant selection

FE settings and participants are eligible for the trial if they meet all of the following inclusion criteria and none of the exclusion criteria. All queries about school eligibility should be directed to the SaFE Study Manager before randomisation.

7.1 Setting inclusion and recruitment

Phase 1: Intervention optimisation: Optimisation of intervention materials (manual, staff training and publicity materials) for use in FE settings with stakeholders, FE students, staff and ALPHA youth group. Recruitment of the participating FE setting will commence prior to study commencement and the site will be purposively sampled based on location in South Wales; sites used in the MRC PHIND funded SaFE project will be excluded. A sample of staff and students with capacity to participate will then be recruited for group interviews. Students under age 16 will be excluded.

Phase 2: Intervention feasibility testing: One college and one 6th form will be recruited for feasibility testing (n=1 college in England, n=1 6th form Wales). FE settings will be purposively sampled based on location in South Wales and Bristol/South Gloucester/North Somerset. No random allocation will occur. Sites used in the MRC PHIND funded SaFE project or optimisation phase (Phase 1) as well as those with current onsite sexual health provision (e.g. STI testing) will not be eligible to take part. We will incentivise FE setting retention by making a payment of £250 at the end of the feasibility testing.

Phase 3: Pilot cRCT: All state funded FE settings including community colleges and 6th forms attached to secondary schools will be eligible to participate, including private and Welsh medium schools. Inclusion criteria: All students aged 16 and older enrolled at participating FE settings.

Exclusion criteria: No FE students aged 16 and older will be excluded. Fieldworkers will support participation for those with learning difficulties or poor English. Schools for those with learning disabilities will be excluded. For this study, settings with existing onsite service provision (e.g. STI testing) will also be excluded from the sampling frame.

Study population: SaFE is designed to be a universal intervention for all students attending FE settings. The majority of FE students are aged 16-24. We will incentivise FE setting retention by making a payment of £500 at the end of the study. In Wales, two colleges and one 6th form will be recruited, and in England two 6th forms and one college will be recruited.

	England	Wales
Feasibility testing	FE college (n = 1)	6th form (n=1)
Pilot cRCT	FE college (n = 1)	6th form (n=1)
	6 th form (n=2)	FE college (n=2)

Eligible settings will be approached via a relevant senior manager (e.g. deputy head, head of pastoral care), identified with the help of the School Health Research Network (for 6th forms in Wales), and Public Health leads and service providers in local authorities in England, and invited to participate. Schools will be emailed of posted a project information sheet, reply enveloped and form indicating if they wish to participate. If necessary, non-responders will be followed up with a reminder and then by a phone call by the Safe Study manager. All interested settings will be visited by the SaFE Study manager and a contact from the intervention delivery team to discuss the trial in more detail and agree a research contract including signing a memorandum of understanding (MoU) describing the roles, responsibilities, timeline of intervention delivery, and assessments before taking part in the study. The MoU will be signed by a member of the senior leadership team, ideally the headteacher/ FE manager, with an additional contact teacher/lead also listed. Any settings that decline before randomisation will be replaced by another setting from the same stratum and geographical area.

